### 3. Evaluation after treatment

Evaluation of curative effects and safety is conducted at the end of the drug therapy, six and twelve months after the treatment, where the evaluation content is the same as that before the trail.

## IX. Statistical analysis

### 1. Methods of statistical analysis

Classified variables are expressed by frequency distribution (case number and percentage). Continuous variables are described through mean, median, minimum, maximum, first and third quartile. The confidence interval of all parameters is the significance level = 0.05. All analyses are conducted with SPSS.

### 2. Contents of methods of statistical analysis

1) General data analysis: demographic variables and baseline characteristics are summarized with mean of descriptive statistic and/or appropriate frequency tables.

2) Evaluation of curative effects: according to follow-up and reexamination results, quality of life, fibroid control and improvement of symptoms are analyzed.

3) Analysis of adverse reactions: assessment of side effects and adverse events during medication.

4) Judgement of relations between adverse events and the tested drug

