## IV. Research design

1. This study is a non-random open-label clinic trial carried out by the department of gynaecology and obstetrics, Peking Union Medical College Hospital.
2. All patients who accorded with inclusion criteria and signed informed consents received sirolimus treatment for at least three months. After drug withdrawal, there patients were followed up for at least one year.
3. There should be at least 25 patients included in this study without an upper limit of included patients.

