## VI. Therapeutic schedule

1. Initial dosage of administration and dosage regimen: take 2mg of sirolimus once a day since the fifth to seventh day of menstruation. After one week of medicine taking, subjects are called for an interview. If a subject has severe adverse reactions and fails to tolerate the drug, her weekly dosage can be reduced to 0.5mg, where the minimum daily dosage should be 1mg / day. If the subject still fails to tolerate the drug, she should quit; if she feel unwell but tolerable, the administration should be continued for another three months. After the three months, evaluate the condition of this subject.
2. Subsequent dosage of administration and dosage regimen: if the condition of a subject is significantly improved after taking 2mg of sirolimus once a day for three months, the initial administration should be continued. If the condition of a subject shows no significant improvement, the dosage should be changed into 2.5mg-3mg once a day. If this subject fails to tolerate the dosage, she should quit this study; if she can tolerate the dosage, this dosage regimen should be executed for three months. After that, her condition should be evaluated again.
3. Iron supplement: if hemoglobin of a subject  $\leq 10.9$  g/dL, she should receive iron supplement in accordance with the standard dosage regimen. However, the iron supplement is not regarded as a part of treatment of this study and will be recorded as a part of drug combination.
4. If the condition of a patient with a rare type of uterine fibroids (including intravenous leiomyomatosis, leiomyomatosis peritonealis disseminate and benign metastasising leiomyomas) is under control with a tolerable drug, the patient can continue this drug therapy after this six-month study.

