### 2. Evaluation during sirolimus treatment

In the first month of treatment, evaluation of adverse reactions is conducted every week. In the third and sixth months, curative effects and safety of sirolimus were assessed.

1) Evaluation of curative effects: sizes of the uterus and fibroids were measured through pelvic MRI. Blood was drawn to monitor the female hormone level and impacts of bleeding and symptoms on daily life of subjects.

2) Evaluation of safety: safety parameters (such as to enquire AE and measure laboratory values, vital signs, thickness of endometrium, abnormal uterine bleeding and sizes of follicular structure including follicle and functional ovarian cysts) are monitored periodically during the study.

3) Treatment compliance: in order to monitor compliance, subjects are asked to keep an E-diary every day. Researchers track each date of studied drug taking in accordance with E-diaries. In each interview, researchers and subjects examine the data integrity of E-diaries together.

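### The only planned adverse-event summary covers the time on drug, although safety is to be evaluated up to 12 months after treatment, so events that start off drug and the outcome of events open at the last dose go unreported

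*Combined protocol and SAP*

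**What the plan says.** Four places in the combined protocol and SAP bear on the safety window.

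- **Analysis.** Section IX.2 item 3, on adverse reactions, plans an "assessment of side effects and adverse events during medication". Item 4 adds a judgement of the relation between adverse events and the drug, with no time window. No other item summarises adverse events.
- **Post-treatment visits.** Section VIII.3 states: "Evaluation of curative effects and safety is conducted at the end of the drug therapy, six and twelve months after the treatment". It continues: "where the evaluation content is the same as that before the trail". The pre-trial list in VIII.1 consists of medical history, personal profile, physical examination, blood count, liver and renal function with lipids, sex hormones, urine and pregnancy tests, and pelvic MRI.
- **Adverse-event enquiry.** This appears in VIII.2, the section on evaluation during treatment, where safety parameters are described with the words "such as to enquire AE and measure laboratory values, vital signs". That section also requires a safety assessment in the third and sixth months.
- **Durations.** Section IV says patients "received sirolimus treatment for at least three months" and, after withdrawal, are "followed up for at least one year". Section VI item 4 adds that, if a rare type is controlled and the drug is tolerated, "the patient can continue this drug therapy after this six-month study".

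**The concern.** Safety is one of the two objectives in section II. Section I says that safety in this indication still has to be established, and section XII describes the use as outside the labelled instructions. For such a drug, whether reactions resolve after stopping, and whether new ones appear, is part of the safety answer.

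The plan schedules visits that could supply this information, but its one adverse-event analysis refers to the time on drug. The efficacy item beside it (IX.2 item 2) draws on follow-up and re-examination results, so the efficacy window reaches into follow-up and the safety window does not.

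Collection has a matching gap. The post-treatment visits inherit a list written for patients who had not yet taken the drug, and that list has no adverse-event question. An event in this period would be recorded only if it came up in the medical history or showed in an examination or laboratory result. Rewording the analysis alone would therefore leave little systematic data to analyse.

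**Working it through.** The plan states no event rate, power or derived sample size that bears on this point, so there is no figure of its own to reproduce. The check compares the sections and then measures the period that is not covered.

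**Step 1: collection against analysis, by period.**

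| Period | Adverse-event enquiry named? | Adverse-event summary planned? |
|---|---|---|
| On drug | Yes (VIII.2) | Yes (IX.2 item 3) |
| End of therapy, at month 3 or 6 | Yes (the VIII.2 assessment coincides) | Yes, for events with onset on drug |
| End of therapy, between assessments | Not named in VIII.3 | Yes, for events with onset on drug |
| 6 and 12 months after treatment | Not named in VIII.3 or VIII.1 | None stated |

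**Step 2: what falls outside.** An event that starts on drug is an event during medication and is counted under item 3, whether or not it has resolved. Two things have no planned summary: events with onset after the last dose, and the later course and outcome of events still open at that point.

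**Step 3: share of minimum follow-up that is off drug.** Inputs are 12 months after withdrawal (section IV) and treatment of *t* months, with *t* = 3 (the section IV minimum) or *t* = 6 (the study length in section VI item 4).

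Off-drug share = 12 / (12 + *t*)

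- *t* = 3: 12/15 = 80%
- *t* = 6: 12/18 = 67%
- *t* = 12: 12/24 = 50%, so the share falls below half for a rare-type patient treated for more than 12 months.

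**Step 4: the same in person-time.** For the minimum of 25 patients (section IV), all followed for the full year:

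- 3-month course: 25 × 3 = 75 person-months on drug, against 25 × 15 = 375 in total.
- 6-month course: 25 × 6 = 150 on drug, against 25 × 18 = 450 in total.

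**Step 5: illustration with assumed risks.** The documents give no rate for post-treatment events. If each of 25 patients independently has risk *p* of at least one, the chance that at least one patient has an event outside the stated window is 1 − (1 − *p*)^25:

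- *p* = 2%: 40%
- *p* = 5%: 72%
- *p* = 10%: 93%

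These values of *p* are assumptions. They show only that such an event is plausible in a study of this size.

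**The case against.** The strongest reply is that the plan excludes nothing. Item 3 does not say that only on-drug events count. The causality item, the safety objective in section II and the safety entry in section III carry no time limit. The descriptive methods in IX.1 are not confined to treatment. VIII.2 speaks of monitoring during the study, and the post-treatment visits do repeat the physical examination and laboratory tests. The study is also descriptive and uncontrolled, and no test, sample size or decision depends on this window.

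Part of this stands. A reader might infer that the plan throws away a year of safety follow-up, and the text does not go that far: it names one window and is silent on the rest. The reply does not close the gap, however. The causality item plans no summary of later events, the VIII.2 wording governs collection and sits under the on-treatment heading, and no section says what will be done with safety findings from the 6- and 12-month visits.

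Three other stronger readings should be set aside.

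- That unresolved events drop out of the analysis. They do not if they began on drug; only their later outcome is unaddressed.
- That even the end-of-therapy visit lacks an adverse-event question. For patients who finish at 3 or 6 months, the VIII.2 assessment falls at the same time and includes one. The gap at that visit concerns patients who stop between assessments.
- That a patient who stops after one week has 52/53 = 98% of follow-up outside the window. This assumes a year of follow-up after early exit. Section IV describes the year of follow-up for patients treated for at least three months, and sections V.C and VI state none for those who quit.

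**Conclusion.** The concern holds in this form: the safety visits extend to 12 months after treatment, the one stated adverse-event summary does not, and the later visits do not name the enquiry needed to support one. Followed as written, the plan answers its safety objective incompletely, mainly on reversibility and on events with off-drug onset.

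The uncovered period is 67% of minimum follow-up for a 6-month course and 80% for a 3-month course, assuming the full 12 months after withdrawal. A reader might take these figures as the proportion of events missed. They are shares of time; without event rates, neither the number of missed events nor any bias in the safety result can be computed. The shares are lower for rare-type patients who continue the drug. The point does not affect the efficacy analysis, but it should be corrected because safety is a stated objective and the visits are already planned.

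**What to change.** Two edits are needed, and neither is enough alone.

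1. **IX.2 item 3.** Summarise side effects and adverse events from the first dose to the 12-month post-treatment evaluation, or to last contact for patients who leave earlier. Show on-drug and off-drug onset separately, and give the outcome of each event as resolved or continuing.
2. **VIII.3.** Add the adverse-event enquiry of VIII.2, including the status of events open at the last dose, to the 6- and 12-month post-treatment visits and to the end-of-therapy visit of patients who stop between scheduled assessments.

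If a wider window was always intended, the same edits state it. The cost is a few sentences and one set of questions at visits already in the plan. The reported event count may rise, and off-drug events are harder to attribute to the drug, which is why the two periods should be displayed separately.

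### The adverse-event summary has no dose, exposure or time dimension, although dose and duration vary by rule, so a crude percentage cannot show at what dose or when harms occurred

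*Combined protocol and SAP*

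**What the plan says.** Section II names safety as the second of two objectives. Section IX.2 covers its analysis in two items: "assessment of side effects and adverse events during medication" and "Judgement of relations between adverse events and the tested drug". Section IX.1 supplies the format: "Classified variables are expressed by frequency distribution (case number and percentage". It adds an interval or significance statement, "The confidence interval of all parameters is the significance level = 0.05". No denominator, time window, dose split or measure of exposure is given.

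Section VI makes dose and duration vary by rule:

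- Women start with "take 2mg of sirolimus once a day".
- For intolerance the dose can be lowered, with a 1 mg/day minimum. A woman who still cannot tolerate the drug leaves.
- If there is no significant improvement at three months, "the dosage should be changed into 2.5mg-3mg once a day". A woman who cannot tolerate that dose also leaves.
- If a rare type of fibroid is under control on a tolerable drug, "the patient can continue this drug therapy after this six-month study". No end date is given.

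Section IV sets a minimum of three months' treatment and at least 25 patients. Under section V.C a woman may withdraw at any time. Section VIII.2 evaluates adverse reactions weekly in month 1 and assesses safety at months 3 and 6. On intake it says: "Researchers track each date of studied drug taking in accordance with E-diaries".

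**The concern.** A percentage of women with an event is readable when everyone takes the same dose for the same time. Here neither holds. The longer a woman is on drug, the more chance she has to record an event, so the percentage mixes toxicity with duration. An event on 2.5-3 mg enters the same numerator as one on 2 mg or on a reduced dose. A harm confined to the raised dose, which nobody reaches before month 3, would be averaged over time spent mostly at 2 mg.

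Section I says sirolimus has not yet been applied to uterine fibroids and that its safety there still has to be verified. A reader will want to know at what dose and after how long harms appeared. The planned summary answers neither question.

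**Working it through.** The plan states no adverse-event rate, dropout figure or derivation of the 25, so there is no figure to reproduce. All rates, dose splits and exposure mixes below are assumptions. The doses, the 3- and 6-month points and the minimum of 25 come from sections IV, VI and VIII.2.

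**1. Dependence on time on drug.** With a constant first-event rate r per woman-month, the chance of at least one event by month T is 1 − exp(−rT).

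| Assumed r | T = 3 | T = 6 |
|---|---|---|
| 0.05 | 14% | 26% |
| 0.10 | 26% | 45% |
| 0.20 | 45% | 70% |
| 0.30 | 59% | 83% |

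Now take 25 women with r = 0.10 and exits unrelated to adverse events:

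- Mix A: 5 stop at one week (0.23 month), 15 at three months, 5 at six. Expected cases = 5 × 0.023 + 15 × 0.259 + 5 × 0.451 = 6.26, or 25%.
- Mix B: 2, 3 and 20 women at the same times. Expected cases = 9.85, or 39%.

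The first-event rate per month at risk is 0.10 in both mixes. The 14-point gap comes from exposure alone.

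**2. Masking of a dose pattern.** Assume 25 women complete six months, 8 are raised at month 3, and the rates are 3 per 100 person-months at 2 mg and 10 at the raised dose.

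- Person-months at 2 mg: 25 × 3 + 17 × 3 = 126. Raised: 8 × 3 = 24, which is 16% of 150.
- Not-raised women: 1 − exp(−0.03 × 6) = 1 − exp(−0.18) = 16.5%.
- Raised women: 1 − exp(−(0.03 × 3 + 0.10 × 3)) = 1 − exp(−0.39) = 32.3%.
- Crude percentage: (17 × 0.165 + 8 × 0.323)/25 = 21.5%, against 16.5% with no dose effect.

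A rate ratio of 3.3 appears as 5 points.

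**3. Women who leave for intolerance.** They have had an event, so they count as cases. Take 20 six-month completers at 0.05 per month and 5 intolerance exits: (20 × 0.259 + 5)/25 = 41%. With no exits, 25 completers would give 26%. Intolerance exits therefore raise the crude figure.

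**4. What a by-dose table can deliver.** In the step 2 scenario the raised dose yields 24 × 0.10 = 2.4 expected events. Two observed events have exact 95% Poisson limits of 0.242 and 7.225. Divided by 24 person-months, these are 1.0 and 30.1 per 100.

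A before/after comparison in the 8 raised women, leaving out the intensively monitored first month, has 8 × 2 = 16 earlier person-months and 16 × 0.03 = 0.48 expected events, set against 2.4. A two-sided exact conditional test at 0.05 has power of about 0.7%.

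**The case against.** **Pooling is not stated.** The plan never says that all events go into one percentage, and it does not forbid tables by dose. That is correct: the defect is an omission. It still matters, because case number and percentage is the only categorical summary the plan supplies.

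**Early leavers.** A reader might infer that women who stop early count as event-free and so make a poorly tolerated drug look safe. Section VI does not support this. Its intolerance exits are triggered by adverse reactions, and step 3 shows that they raise the percentage. Dilution is confined to exits unrelated to adverse events and to later events that early leavers had no time to show.

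**Unlimited exposure.** A reader might also infer that exposure in the analysis runs from one week without limit. Continuation is restricted to controlled rare-type patients and is placed after the six-month study. Whether their later events count is undefined. The intolerance exit follows a dose reduction made after the one-week interview, so it comes later than one week.

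**A dose table cannot show a dose effect.** This stands. Dose goes down for intolerance and up for non-response, without randomisation, so any contrast is confounded with tolerance, response and time on drug. Raised women have also come through the first three months. Step 4 shows how sparse the data would be. It follows that the table is descriptive; it does not follow that dose and exposure should go unreported.

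**The data are not all there.** This stands in part. The E-diary is described as tracking intake dates; dose is not mentioned, and no diary after month 6 is described.

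**Conclusion.** The concern holds as a reporting gap in one of the two objectives. Applied as written, the plan gives a crude percentage that depends on time on drug and cannot locate harms by dose or time. For scale, the same assumed rate of 0.10 per month gives 26% or 45% depending on whether treatment lasts three or six months, and a 3.3-fold dose difference in the assumed scenario shows as 5 points. These sizes rest on constant rates and on assumed dose splits and exposure mixes; the direction of the time effect does not. It would be wrong to conclude that the crude percentage understates intolerance, or that a by-dose analysis would establish a dose effect at this sample size. The change is cheap and should be made.

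**What to change.** In section IX.2, item 3:

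- Keep the crude number and percentage of women with an event.
- Add a table of events and person-months by dose being taken at onset (reduced, 2 mg, 2.5-3 mg) and by window (0-3 and 3-6 months), with rates per 100 person-months and exact Poisson limits.
- List events after month 6 separately, and report the numbers of dose reductions and intolerance exits.
- Label all by-dose results descriptive, and make no inferential before/after comparison.
- Note beside the table that weekly questioning in month 1 inflates early counts relative to later months.

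In section VIII.2, record the dose as well as the date in the E-diary, and put dose at onset on the adverse-event form. For women who continue after month 6, state whether intake and events are still recorded.

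Before the reduced-dose category is defined, the sponsor must reconcile two statements in section VI, item 1: the reduction is worded as a weekly dosage of 0.5 mg, while the minimum is 1 mg per day. The three-month minimum treatment in section IV must also be reconciled with the earlier exits allowed in sections V.C and VI.

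The cost is one table and one extra data field. The drawback is very wide intervals in the smaller dose groups.

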## X. Measures of quality control

- 1) Supervision by the project leader
- 2) Establish a standard evaluation method, unify criteria of diagnosis and effect assessment etc.
- 3) Formulate plans for monitoring and treatment of adverse reactions
- 4) All researchers receive training before this study
- 5) Assign quality controllers and develop a plan for quality control with regular inspections
- 6) Devise a follow-up plan and system

## XI. Expected research results

After this study, its research results will be published in a paper and subjects will be informed of these results.

## XII. Potential risks, benefits or advantages of this study

As a drug coming into the market for years, it is applied to this study beyond instruction, where physicians know that its benefits outweigh its risks and have no other choice. For subjects in this study, their symptoms can be relieved, their quality of life can be improved, their uterus can be retained and surgery-related complications and psychological harm caused by loss of fertility can be avoided. During this study, all tested drugs are free and subjects should bear risks of the treatment.

## XIII. Expected effects and preservation and confidentiality of data etc

According to the informed consent: personal information of subjects is strictly confidential in this study. Results of this study may be published in a paper, but personal information of subjects, including their names, will not appear in the paper. All data related to this study will be kept by Peking Union Medical College Hospital and strict confidentiality measures will be established.

## XIV. Measures to protect subjects and minimize risks

In the whole course of this study, safety supervision of subjects will be carried out by experts and professors from the department of gynaecology and obstetrics of this hospital to strictly control diagnostic criteria and treatment indicators of symptomatic uterine fibroids and myomatosis, leading to collected clinical data according with the international diagnostic standard and favorable guarantee of various patients in treatment.
